**AN INVESTIGATION INTO THE RELATIONSHIP BETWEEN HEMORRHOID
DISEASE AND THE USE OF SMARTPHONES IN THE LAVATORY**

Unique Protocol ID: 12/22/2017 – 051

Date: February 11, 2018

Tarih :
Versiyon :

STUDY PROTOCOL

The objective of medical research: A changing world not only brings about different lifestyles and diverse eating habits, it also changes the causes and courses of known diseases. The goal of this study is to examine the relationship between hemorrhoids, a common complaint, and the use of smartphones, also a common feature of modern life, in the lavatory.

The scientific basis and validity of medical research: As is known, hemorrhoidal disease is a frequently observed disease of the lower rectum and anal region that seriously impairs the patient's quality of life. Its worldwide prevalence is reported to be approximately 4.4% [1, 2]. One out of every two people over the age of 50 is reported to experience symptomatic hemorrhoidal disease, with increased frequency with age, especially after the age of 45 [3].

The underlying physiopathological event is vascular enlargement of the lower rectum [2]. Hemorrhoids are classified as internal or external, and it is assumed that the same pathological mechanisms operate in both types (**Figure 1**). Accepted pathological mechanisms and predisposing factors are summarized as follows:

Reduced venous drainage

Many researchers believe that foods low in fiber reduce stool caliber and cause an increase in straining during defecation, thereby increasing the pressure on the anal region [4]. The increased pressure in the anal region leads to prolapsed hemorrhoids and at the same time inhibits venous return. The inhibition of venous return further increases the prolapse of hemorrhoids thus rendering it symptomatic. Hemorrhoids may also develop via the aforementioned mechanism in situations where pressure is augmented such as pregnancy and increased anal sphincter tone. Sitting on the toilet for a long time (for example, while reading a newspaper) has been determined to inhibit venous drainage (the tourniquet effect) [5]. Together with aging, the weakening-loosening of the connective tissue supporting hemorrhoid papillae accelerates the development of hemorrhoidal disease.

Straining and constipation

Chronic constipation and straining have long been recognized as the primary cause of hemorrhoidal disease. Although there has been a number of studies that support this, data that do not support this conclusion have also been reported [4-6]. It is generally accepted that

Tarih :

Versiyon :

increased pressure in the anal canal is greater in those with hemorrhoidal disease and that this pressure decreases following surgery.

Pregnancy

The effect of pregnancy on the development of hemorrhoids is evidenced by the postpartum disappearance of hemorrhoidal symptoms. Increased intra-abdominal pressure and hormonal changes experienced during pregnancy may cause hemorrhoids [7-9].

Portal hypertension and anorectal varices

Although anorectal varices are often accompanied by portal hypertension, symptomatic hemorrhoids are not often observed in patients with portal hypertension [10, 11]. In cases of bleeding the varices should be sutured. Hemorrhoidal disease also regresses with the resolution of underlying liver problems.

Other risk factors

Other factors believed to be related to the development of hemorrhoids include the following: Higher socio-economic status, chronic diarrhea, family history, obesity, anal intercourse, hepatic diseases, inflammatory bowel diseases, rectal surgery, colon cancer, and spinal surgery.

Given the pathophysiological and accelerating factors described above, an increase in hemorrhoidal disease in modern society is to be expected. People today prefer a more sedentary lifestyle and partake of a low-fiber diet richer in high calorie/high fat foods compared with previous generations. In addition, smartphones have invaded nearly every aspect of daily life. In clinical observations, the investigators have found that the use of mobile phones in the lavatory has become a habit for some people. This habit, which increases the time spent on the toilet, is also thought to lead to an increase in pressure on the anal region and straining during defecation. The investigators have not encountered any studies in the literature investigating the relationship between these two situations (smartphone use in the lavatory and the development of hemorrhoids). There is therefore a gap in the literature examining this relationship. Researching this relationship by means of the scientific method should reveal important information. The basic research question of the present study is thus designed to determine to what extent the use of smartphones increases time spent in the lavatory and whether there is an association between this increase in time and hemorrhoidal disease.

Tarih :

Versiyon :

Study protocol, methods, and procedures:

This clinical study will be conducted with a cross-sectional design based on retrospective observation (Figure 2). Apart from the target population there will be a control group. In retrospective studies the selection of the control group is of the utmost importance. Other than the risk factor that is being investigated (the use of smartphones), factors that affect the development of hemorrhoidal disease are similar for the study group and the control group, thus minimizing confounding factors. The control group, as will be noted, will thus have a social environment resembling that of the study group. It should also be noted that members of the control group will be completely healthy, with no health problems (e.g., hearing or visual disturbances) that could affect their use of the risk factor (smartphones).

The study population consists of patients with complaints of hemorrhoids referred to the General Surgery Polyclinic. The control group is comprised of healthy volunteers with no complaints of hemorrhoids (Figure 3). Both the study group and the control group will include persons of both genders between 16 and 65 years of age. Informed consent will be obtained from patients and volunteers, following which a Likert-type survey will be given to each participant to complete (Table 1, questionnaire form). A pilot study will be conducted for the factor analysis of the questions to be asked in the questionnaire. In the pilot study, the target will be to survey 100 patients. After the factor analysis is performed on 100 patients, the questionnaire that is developed will be used in the main study.

As no prevalence study was previously performed for the sample size, it will be calculated based on the prevalence (frequency of smartphone use in the lavatory in the study group and the control group) determined after the pilot study, accepting a type I error of 0.005 and a type II error of 0.20 (80% test power).

The doctor who performs the examinations will be blinded to the questionnaire results. After completion of the questionnaire, the patient's anal region and rectum will be examined by a general surgeon and the presence or absence of hemorrhoids will be noted. Subsequently, if hemorrhoids are present, they will be recorded as either external or internal. Internal hemorrhoids will then be staged as first-degree, second-degree, third-degree, or fourth-degree, according to standard textbook definitions [2].

Primary endpoints of the study:

1) determination of the stage of hemorrhoids in patients with complaints of hemorrhoids

Tarih :

Versiyon :

2) frequency and duration of smartphone use in the lavatory for those with smartphones

Statistical Data Analysis:

All data will be analyzed using the SPSS version 20 package program. The data will consist of categorical nominal and continuous numerical variables. Frequency and percentages will be given for categorical and nominal variables. Following testing for normal distribution of numerical variables, those with normal distribution will be expressed as mean \pm standard deviation, while variables without normal distribution will be expressed as median value and minimum - maximum. The relationship between the risk factor and the outcome variable will be assessed using the Chi-square test. The difference between hemorrhoid stages in terms of exposure times to the risk factor will be determined by ANOVA or the Kruskal-Wallis test. A *p* value of 0.05 will be accepted as statistically significant.

Tarih :

Versiyon :

REFERENCES

2. Lowney JK, Fleshman JW Jr. Benign disorders of the anorectum (pelvic floor, fissures, hemorrhoids, and fistulas). In: Zinner MJ, Ashley SW, eds. *Maingot's Abdominal Operations*. 11th ed. New York: McGraw-Hill; 2007: 663-693.
7. Wald A. Constipation, diarrhea, and symptomatic hemorrhoids during pregnancy. *Gastroenterol Clin North Am*. 2003; 32: 309-322, vii.
10. Bernstein WC. What Are Hemorrhoids and What Is Their Relationship to the Portal Venous System. *Diseases of the Colon & Rectum*. 1983; 26: 829-834.

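### The health and smartphone-ability rule is stated for controls only and can bias the crude comparison, modestly and, on the likelier reading, toward understating the association

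*Protocol*

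**What the plan says.** The section of the Protocol headed Study protocol, methods, and procedures sets the control rule: "members of the control group will be completely healthy, with no health problems (e.g., hearing or visual disturbances) that could affect their use" of smartphones. The population description that follows repeats it: "The control group is comprised of healthy volunteers with no complaints of hemorrhoids".

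Cases are described differently: "The study population consists of patients with complaints of hemorrhoids referred to the General Surgery Polyclinic". No health or smartphone-ability condition is attached to them. The one criterion stated for both arms is this: "Both the study group and the control group will include persons of both genders between 16 and 65 years of age".

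The same methods section asserts that "factors that affect the development of hemorrhoidal disease are similar for the study group and the control group", but it gives no matching or restriction procedure for cases. The second primary endpoint is "frequency and duration of smartphone use in the lavatory for those with smartphones". That limits an endpoint to phone owners; it does not set who may enter the study.

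The Protocol (Statistical Data Analysis) and the SAP (Statistical Analysis) both test the relationship between exposure and outcome with a Chi-square test. The SAP adds a binary logistic regression. Its sample-size section uses 22 independent variables but does not list them.

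**The concern.** The SAP calls this a case-control study. In such a study the controls should show how common the exposure is in the population that produced the cases. If people are removed from the control arm only, and they differ from the rest in lavatory phone use, the crude OR shifts even when there is no true association.

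The rule can be read in two ways.

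- **Narrow:** only problems that affect phone use are excluded. Every control is then able to be exposed, while some cases may not be. This pulls the OR down.
- **Broad:** controls have no illness at all. Conditions that the Protocol lists as hemorrhoid risk factors are then removed from controls and kept in cases. Examples are constipation ("Chronic constipation and straining have long been recognized as the primary cause of hemorrhoidal disease"), chronic diarrhea and inflammatory bowel disease. This works against the stated similarity of the groups. The OR rises if affected people use phones in the lavatory more than others, and falls if they use them less.

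At stake is the size of the crude estimate. A larger sample does not remove this kind of bias.

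**Working it through.** **Inputs from the SAP (Calculation of Sample Size).** Pilot exposure is 36.4% in cases and 13.2% in controls. The group size is 10 × 22 / 0.269 = 817.8, so 818, which reproduces the SAP's figure. The sample-size calculation does not use the health rule and neither supports nor refutes this point.

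**Pilot crude OR.** (0.364/0.636) / (0.132/0.868) = 0.5723/0.1521 = 3.76.

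**Assumptions, not in the documents.** These are f, the share of cases unable to use a phone; c, the share of cases with a condition excluded from controls; e, the exposure among those affected; and the condition's own OR for hemorrhoids. Rejection rates are for the Chi-square test at 0.05 with 818 per group.

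**Narrow reading.** Case exposure is multiplied by (1 − f); control exposure stays at 13.2%.

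| f | Case exposure, true OR 1 | Observed OR | Rejection, either direction | Rejection toward harm (nominal 2.5%) | Pilot OR becomes |
|---|---|---|---|---|---|
| 2% | 12.9% | 0.98 | 5.3% | 1.7% | 3.65 |
| 5% | 12.5% | 0.94 | 6.8% | 0.9% | 3.48 |
| 10% | 11.9% | 0.89 | 12.7% | 0.3% | 3.20 |

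The last pilot entry, for example, is 0.364 × 0.90 = 0.3276, and (0.3276/0.6724)/0.1521 = 3.20. The excess rejections all point toward a protective effect.

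**Broad reading.** Case exposure = c·e + (1 − c) × 0.132, with the condition absent in controls.

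- c = 5%, e = 40%: 0.02 + 0.1254 = 0.1454; OR = (0.1454/0.8546)/0.1521 = 1.12; rejection about 12%.
- c = 2%, e = 25%: exposure 13.4%, OR 1.02.
- c = 5%, e = 5%: exposure 12.8%, OR 0.96. The direction therefore depends on e.

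**How much of the 1.12 is due to the rule.** A genuine risk factor would confound the crude OR without any health rule. Keep c = 5% in cases (odds 0.05/0.95 = 0.0526), e = 40%, and delete the rule.

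- Condition's own OR 2: odds in controls 0.0263, prevalence 2.56%. Control exposure = 0.0256 × 0.40 + 0.9744 × 0.132 = 13.89%. The crude OR without the rule is 1.06 (1.055), so the rule's factor is 1.119/1.055 = 1.06.
- Condition's own OR 3: prevalence in controls 1.72%, control exposure 13.66%. The crude OR without the rule is 1.08 (1.075), so the rule's factor is 1.119/1.075 = 1.04.

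If the condition were unrelated to hemorrhoids, the whole 1.12 would come from the rule.

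**Complaint patients without hemorrhoids.** After the examination, "the presence or absence of hemorrhoids will be noted". If 10-30% of the complaint group were counted as absent, 1.12 would become 1.11-1.09 and 0.89 would become 0.90-0.91, which is little change.

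**Can covariates repair it?** Under a one-sided rule the condition occurs in no control, so its logistic coefficient has no finite estimate and the affected cases drop out of the comparison. At c = 5%, e = 40% the standard error of the smartphone log OR is 0.143 crude. Using only the 818 × 0.95 = 777 unaffected cases it is 0.148, which is exactly what the adjusted model gives. Adjustment here is deletion of those cases.

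**The case against.** The strongest case on the other side has five parts.

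1. **The estimate of how far phone use raises risk belongs to the logistic regression, not the Chi-square test.** This stands. Every bias figure above is for a crude comparison. No bias in the regression has been shown, and its unnamed covariates leave the question open either way.
2. **On the narrow reading the bias is conservative.** This stands. A reader might infer that the rule manufactures support for the hypothesis, but on that reading it makes a false finding of harm less likely than 2.5%.
3. **The broad reading sits badly with its own paragraph.** The sentence ties health to phone use, and the paragraph says that risk factors are similar. This favours the narrow reading but does not settle it, because the population description says healthy volunteers without qualification.
4. **Much of the broad-reading excess is ordinary confounding.** This stands for conditions that are true risk factors: the crude OR would still be 1.06-1.08 with the rule deleted.
5. **Figures 2 and 3 and the questionnaire are not reproduced here, and a parallel rule for cases could be in them.** This is possible, so the point is confined to the readable text. The age cap of 65 and the self-completed questionnaire also limit how many cases could be unable to use a phone.

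The one-sided rule in the text remains. Asserted similarity is not an eligibility criterion, and owning a smartphone is not the same as being able to use one.

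**Conclusion.** The point holds as a modest, inexpensive design improvement. In the readable text, controls alone are selected on health and on ability to use a smartphone, and this can bias the crude Chi-square comparison.

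On the favoured narrow reading the OR is understated, by a factor of 0.98-0.89 under no association with 2-10% of cases unable to use a phone. On the broad reading the rule contributes about 1.04-1.06 when 5% of cases are affected, 40% of those are exposed and the condition's own OR is 2-3. With low exposure among those affected, the shift is downward. The documents give none of these shares, so the actual size cannot be determined, and neither can the direction while both readings remain open.

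Two stronger conclusions are not supported. The rule does not account for the pilot difference: the shifts calculated here are small beside an OR of 3.76. Nor do the documents show that the planned logistic regression is biased; that depends on 22 covariates they do not name.

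**What to change.** 1. Apply the same smartphone-ability criterion to cases and controls.
2. Either delete the complete-health requirement for controls, leaving absence of hemorrhoid complaints as their only extra condition, or apply one explicit list of health exclusions to both groups. In the illustration, the same exclusion in both groups returns a null OR to 1.00. Deleting the requirement leaves only ordinary confounding for the regression to handle.
3. If Figures 2 and 3 already give cases a parallel rule, say so in the text; one sentence would be enough.
4. Report the adjusted OR from the planned logistic regression as the main result and the Chi-square test as descriptive.
5. Do not use covariate adjustment in place of symmetric eligibility, since adjusting for a condition that no control can have only discards the affected cases.

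The cost is revised eligibility wording and the choice of which planned analysis leads. The downside is a slightly narrower case population or slightly slower recruitment.

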**AN INVESTIGATION INTO THE RELATIONSHIP BETWEEN HEMORRHOID
DISEASE AND THE USE OF SMARTPHONES IN THE LAVATORY**

Unique Protocol ID: 12/22/2017 – 051

Date: February 11, 2018

Statistical Analysis

All data will be analyzed using the SPSS package program (version 20). The data will consist of categorical, nominal, and continuous numerical variables. Frequency and percentage rates will be given for categorical and nominal variables. Following testing for normal distribution, variables with normal distribution will be expressed as mean \pm standard deviation, while those that do not exhibit normal distribution will be expressed as median and minimum – maximum values. The relationship between risk factor and outcome variable will be evaluated using the Chi-square test. The effect of smartphone use on the presence or absence of hemorrhoids will be analyzed using the Binary Logistic Regression method. Any difference in the degree of hemorrhoids with respect to the duration of exposure to the risk factors will be determined by ANOVA or the Kruskal-Wallis test. A *p*-value of less than .05 will be considered statistically significant.

Calculation of Sample Size

According to the results of the pilot study, 36.4% of the population with hemorrhoidal disease use a smartphone for at least 2 minutes while in the lavatory. In the control group, this percentage was only 13.2%. Since this is a case-control study, the investigators first calculated the number of cases required to calculate the prevalence of a group with hemorrhoidal disease as per the below:

$$n = \frac{Z^2 p(1-p)}{d^2} \quad n = \frac{1.96^2 * 0.364(1-0.364)}{0.05^2} \quad N = 355.7$$

According to the above, in order to estimate a 5% difference in effect size, with an error rate of 5% and 80% power, at least 356 patients are needed. However, in this study, the sample for the logistic regression analysis needs to be calculated in order to investigate to what extent the use of a smartphone during defecation increases the risk of hemorrhoids.

According to analyses performed using the pilot study data, the percentage of the whole population who use a smartphone for at least 2 minutes while in the lavatory is 26.9%. In the logistic regression analysis, in order to determine whether or not smartphone use during defecation (the independent variable) has an effect on the presence or absence of hemorrhoidal disease (the dependent variable), the approach suggested by Peduzzi et al. (1) is as per the below:

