$$N = 10 k / p$$

where

P = the rate of positive or negative events in the population

K = the number of independent variables.

$$N = 10 * (22 / 0.269) = 817.8$$

According to these calculations, calculating the prevalence of smartphone use in the lavatory among the hemorrhoid patient population and measuring the effect of this habit on hemorrhoid development requires 818 patients and the same number of controls. Taking into account the possibility for incomplete or incorrect questionnaires by adding 10% loss to this figure results in a total of $818 + 81 = 899$ participants needed.

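### Does the type I error of 0.005 in the protocol's sample-size sentence conflict with the 0.05 used everywhere else in a way that needs a change?

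*Protocol*

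**What the plan says.** The protocol, under its study methods and procedures, defers the sample size until the pilot has given the "frequency of smartphone use in the lavatory in the study group and the control group". It fixes the design errors in advance: "accepting a type I error of 0.005 and a type II error of 0.20 (80% test power"). It does not say whether the level is one- or two-sided.

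Four other statements bear on the error level:

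- Protocol, Statistical Data Analysis: a *p* "value of 0.05 will be accepted as statistically significant".
- SAP, Statistical Analysis: a *p* "value of less than .05 will be considered statistically significant".
- SAP, Calculation of Sample Size, formula for the number of cases: the numerator is "1.96^2 * 0.364(1-0.364"), so Z = 1.96.
- SAP, same section, the sentence that interprets the result: "with an error rate of 5% and 80% power, at least 356 patients are needed".

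The SAP then sets this figure aside as insufficient for the logistic regression and takes its final number from another rule: "N = 10 * (22 / 0.269) = 817.8", rounded up to 818 and raised to 899 for unusable questionnaires. The two documents carry the same date. Neither mentions a stricter level for sizing, a multiplicity adjustment, or a change from 0.005 to 0.05.

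**The concern.** The type I error is a core design parameter, and here two stated values differ tenfold. The conflict lies within the protocol itself as well as between protocol and SAP, so it cannot be put down to the SAP being a later document.

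If 0.005 were the true design level, three things could be at stake. The sample might have been calculated too small. The 80% power, which the protocol pairs with 0.005, might not describe the test that will be run. Results with *p* between 0.005 and 0.05 might be declared significant against the design intent. A reader who tries to reproduce the sizing from the protocol sentence would also not arrive at the SAP's figures.

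**Working it through.** **Inputs.** From the SAP, Calculation of Sample Size: p = 0.364 in cases, 0.132 in controls, d = 0.05, Z = 1.96, k = 22, overall exposure 0.269. From the protocol: type I error 0.005, power 80%. Assumption: levels are two-sided, which neither document states; Z = 1.96 implies it, since 2(1 − Φ(1.96)) = 0.0500.

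**1. The SAP's 356.** The formula is n = Z²p(1 − p)/d², with p(1 − p) = 0.364 × 0.636 = 0.2315.

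- Z = 1.96 (two-sided 0.05): 3.8416 × 0.231504/0.0025 = 355.7, so 356. This matches the SAP.
- Z = 2.807 (two-sided 0.005): 729.6, so 730.
- Z = 2.576 (one-sided 0.005): 614.4, so 615.

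Only 0.05 reproduces the stated figure. This is a confidence-interval precision formula, so Z sets a confidence level; the formula has no power term.

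**2. The final number.** N = 10k/p = 10 × 22/0.269 = 817.8, so 818; 818 + 81 = 899. There is no error rate and no power in this rule, so the choice between 0.005 and 0.05 cannot move it.

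**3. The calculation the protocol sentence describes.** Neither document carries out a two-group calculation, but it shows what the 0.005 would have meant. Per group, with p̄ = (0.364 + 0.132)/2 = 0.248:

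n = [z(1−α/2)·√(2p̄(1 − p̄)) + z(0.80)·√(p1(1 − p1) + p2(1 − p2))]² / (p1 − p2)²

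- α = 0.05: (1.1970 + 0.4951)²/0.232² = 53.2, so 54 per group.
- α = 0.005: (1.7143 + 0.4951)²/0.232² = 90.7, so 91 per group.

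With 91 per group, power is 80.2% at 0.005 and 95.8% at 0.05. Sizing at the stricter level and testing at 0.05 errs on the safe side.

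**4. Power with the planned numbers.** The SAP can be read as 818 per group or as 899 in total. On the second reading, assuming equal groups and 10% unusable, 899/2 × 0.9 gives about 404 per group. Power for 36.4% against 13.2% is above 99.9% at both levels on both readings.

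**5. Which level governs the tests.** Both significance rules say 0.05. No test in either document refers to 0.005.

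**The case for a change.** The best case for acting is that a tenfold discrepancy in a type I error should not stand unexplained, whatever its effect. The documents do not confirm a misprint, and the pair of 0.005 and 80% power does not describe the declared test. The number also matters to anyone sizing a study this way: 54 per group, adequate at 0.05, would have only about 49% power at 0.005. All of this is accurate as a description of the text.

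There is also one place where 0.005 would have had an effect. In the SAP's precision formula it gives 730 cases instead of 356. A sample of 818 cases covers that; about 450 cases, if 899 is the total in equal groups, does not. So the 356 is unaffected only if 0.05 was the intended level.

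What stands is limited. That formula concerns how precisely exposure is estimated among cases, not a test. With 404 usable cases the half-width would be 2.807 × √(0.231504/404) = 0.067 at the 99.5% confidence level, against 1.96 × √(0.231504/404) = 0.047 at 95%. The cost would be an interval of about ±6.7 points rather than ±5, at a confidence level that no analysis in the plan calls for. Nor is a reader left guessing: the protocol sentence looks ahead to a calculation, and the SAP reports the one that was made, with its Z and its 5% stated.

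**Conclusion.** The inconsistency is genuine but clerical in effect, and correcting it gains nothing for the study. One figure, 0.005, stands against four consistent uses of 5%. It was not used in the only sizing step that has an error rate, it cannot enter the rule that produced 818 and 899, and it does not govern any test. An analyst following either document would test at 0.05. Sample size, analyses and conclusions are the same whether the figure is corrected or left.

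This rests on two-sided levels, on the SAP's pilot rates of 36.4% and 13.2%, and, for the smaller reading of 899, on equal groups with 10% unusable. Whether 0.005 is a misprint for 0.05 cannot be settled from the documents, but nothing in the plan depends on the answer. The ambiguity over whether 899 counts all participants, and the attribution of 80% power to a precision formula, are separate matters that this point does not decide.
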